6.5.1 Description of Activities

For all study centers participating at the CARE Crohn's study (Phase IIIb) a follow-up in the PMOS is provided.

6.5.2 Product Supply

Abbott will not supply any product, because it is a postmarketing observational study. Adalimumab is used according to the approved marketing label and is to be prescribed by the physician under usual and customary practice of physician prescription according to the §47 AMG (German Arzneimittelgesetz).

7 Adverse Events

7.1 Adverse Event Definition and Serious Adverse Event Categories

An adverse event (AE) is defined as any untoward medical occurrence in a patient, which does not necessarily have a causal relationship with their treatment. An adverse event can therefore be any unfavorable and unintended sign (including an abnormal laboratory finding), symptom, or disease temporally associated with the use of a medicinal product, whether or not the event is considered causally related to the use of the product.

Such an event can result from use of the drug as stipulated in the labeling, as well as from accidental or intentional overdose, drug abuse, or drug withdrawal. Any worsening of a pre-existing condition or illness is considered an adverse event.

If an adverse event meets any of the following criteria, it is considered a **serious adverse event (SAE):**

Death of Subject An event that results in the death of a subject.

Life-Threatening An event that, in the opinion of the investigator, would have resulted in immediate fatality if medical intervention had not been taken. This does not include an event that would have been fatal if it had occurred in a more severe form.

Hospitalization An event that results in an admission to the hospital for any length of time. This does not include an emergency room visit or admission to an outpatient facility.

Prolongation of Hospitalization An event that occurs while the study subject is hospitalized and prolongs the subject's hospital stay.

Congenital Anomaly An anomaly detected at or after birth, or any anomaly that results in fetal loss.

Persistent or Significant Disability/Incapacity An event that results in a condition that substantially interferes with the activities of daily living of a study subject. Disability is not intended to include experiences of relatively minor medical significance such as headache, nausea, vomiting, diarrhea, influenza, and accidental trauma (*e.g.*, sprained ankle).

Important Medical Event Requiring Medical or Surgical Intervention to Prevent Serious Outcome An important medical event that may not be immediately life-threatening or result in death or hospitalization, but based on medical judgment may jeopardize the subject and may require medical or surgical intervention to prevent any of the outcomes listed above (*i.e.*, death of subject, life-threatening, hospitalization, prolongation of hospitalization, congenital anomaly, or persistent or significant disability/incapacity). Examples of such events include allergic bronchospasm requiring intensive treatment in an emergency room or at home, blood dyscrasias or convulsions that do not result in inpatient hospitalization, or the development of drug dependency or drug abuse.

Spontaneous Abortion Miscarriage experienced by study subject.

Elective Abortion Elective abortion performed on study subject.

7.2 Severity

The physician will use the following definitions to rate the severity for any adverse event being collected as an endpoint/datapoint in the study and for all serious adverse events.

Mild The adverse event is transient and easily tolerated by the subject.

Moderate The adverse event causes the subject discomfort and interrupts the subject's usual activities.

Severe The adverse event causes considerable interference with the subject's usual activities and may be incapacitating or life-threatening.

7.3 Relationship to Pharmaceutical Product

The physician will use the following definitions for any adverse event being collected as an endpoint/datapoint in the study and for all serious adverse events, to assess the relationship of the adverse event to the use of the pharmaceutical product:

Probably Related An adverse event has a strong temporal relationship to study drug or recurs on re-challenge and another etiology is unlikely or significantly less likely.

Possibly Related An adverse event has a strong temporal relationship to the study drug and an alternative etiology is equally or less likely compared to the potential relationship to study drug.

Probably Not Related An adverse event has little or no temporal relationship to the study drug and/or a more likely alternative etiology exists.

Not Related An adverse event is due to an underlying or concurrent illness or effect of another drug and is not related to the study drug (*e.g.*, has no temporal relationship to study drug or has a much more likely alternative etiology).

If an investigator's opinion of possibly, probably not, or not related to pharmaceutical product is given, an alternate etiology must be provided by the investigator for the adverse event.

7.4 Serious Adverse Event Collection Period

Serious adverse events will be reported to Abbott from the time the physician obtains the patient's authorization to use and disclose information (or the patient's informed consent) until 30 days or 5 half-lives, whichever is longer, following the intake of the last dose of physician-prescribed treatment.

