6.4 Study Duration

The observation period for each individual patient starts with the administration of the initial dose of Adalimumab and ends after 60 months.

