7.5 Serious Adverse Event Reporting

In the event of a serious adverse event, whether related to Abbott product or comparator, (if applicable) or not, the physician will notify the Abbott contact person identified below within 24 hours of the physician becoming aware of the event.

Any adverse drug reaction that occurs is recorded by the treating physician using a separate "Adverse drug reaction report" form, labeled 'Bericht über unerwünschte Arzneimittelwirkungen'.

In case of a severe adverse event this form is sent by the treating physician within 24 hours to [name], Abbott GmbH & Co. KG, [name], [contact], [contact]).

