Each study center receives either online permission to a database or binders with a set of sheets for data collection, depending on the technical equipment of the centre. The required data should be entered in to the data sheets using the physicians' documentation. Any observation of an adverse event in the time period up-to 60 months, beginning with the initiation of HUMIRA® therapy, must be documented on the "Adverse Event Form", labeled 'Bericht über unerwünschte Ereignisse' and checked for severity. If the event fulfills the serious criterion (Serious Adverse Event) the "Adverse drug reaction report" form, labeled 'Bericht über unerwünschte Arzneimittelwirkungen' must be completed in addition.

10 Data Analysis Plans

All statistical analysis procedures are described in detail in a statistical analysis plan. This plan will be established by the biometric before the database will be opened for the first interims analysis, and signed by the sponsor, the principle investigator and the biometric.

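### Sections 7.4 and 9 set different windows for serious adverse events, and section 7.5 mixes serious with severe, so late events may be reported unevenly between sites

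*Protocol*

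**What the plan says.** Four places in the protocol bear on this.

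- **Section 7.4** has SAEs reported to the sponsor "from the time the physician obtains the patient's authorization to use and disclose information (or the patient's informed consent"). The end of the period is set separately: "until 30 days or 5 half-lives, whichever is longer, following the intake of the last dose of physician-prescribed treatment". It gives no month-60 limit and no half-life.
- **Section 9** covers "Any observation of an adverse event in the time period up-to 60 months". It counts from the first dose and has each such event entered on the adverse event form. The adverse drug reaction (ADR) form is then required in addition: "If the event fulfills the serious criterion (Serious Adverse Event"). Nothing here depends on the date of the last dose.
- **Section 6.4** matches section 9: "The observation period for each individual patient starts with the administration of the initial dose of Adalimumab and ends after 60 months". It makes no exception for patients who stop.
- **Section 7.5** opens with 24-hour notification: "In the event of a serious adverse event, whether related to Abbott product or comparator, (if applicable) or not". It then describes the ADR form as the record for adverse drug reactions, and adds: "In case of a severe adverse event this form is sent by the treating physician within 24 hours".

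Section 7.2 defines severe as the top grade of an intensity scale. Seriousness has its own criteria in section 7.1.

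**The concern.** A site with a patient who stopped adalimumab two years ago and now has a serious event gets two answers. Under 7.4 the reporting period has closed, while under section 9 the event must still be documented on both forms. For a patient still treated at month 60 the mismatch reverses, because 7.4 runs on after observation has ended. The trigger word adds a second inconsistency. A hospital admission for an event of moderate intensity is serious but not severe, so the last sentence of 7.5 does not call for its form within 24 hours.

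Long-term safety is part of the primary objective (section 5), and safety assessment is the first aim listed in section 10.4. The analysis uses all documented patients (section 10.2), and missing values are not replaced (section 10.3). If sites differ in what they record after treatment stops, that difference passes straight into the long-term safety rates.

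**Working it through.** The protocol gives no figure on this point, so there is none to reproduce. The check is a comparison of the text, followed by a bound on the time affected.

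**1. The two windows**

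| | Section 7.4 | Section 9 |
|---|---|---|
| Duty | Report SAEs to the sponsor | Document all adverse events; add the ADR form if serious |
| Start | Consent or authorization | First dose |
| End | Longer of 30 days or 5 half-lives after last dose | Up to 60 months |
| Patient stops early | Closes after the post-dose period | Stays open to month 60 |
| Patient on drug at month 60 | Continues past month 60 | Closes |

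The windows differ at both ends. The start matters little: between consent and first dose, 7.4 simply applies. The end matters more. Section 6.5 lists discontinuation and restart among the follow-up data, so some documentation off drug is foreseen.

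**2. The 24-hour trigger and the form**

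| | Applies to |
|---|---|
| 7.5, first sentence: notify within 24 hours | Every serious event, related or not |
| 7.5, middle: ADR form | Any adverse drug reaction |
| 7.5, last sentence: send the form within 24 hours | A severe event |
| Section 9: ADR form | Every serious event |

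A serious event of mild or moderate intensity is still notified within 24 hours and still gets the form. What is left open is whether the form itself is due within 24 hours. For a serious event judged unrelated to the drug, 7.5 and section 9 also differ on whether this is the right form.

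**3. Upper bound on the time affected**

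Inputs: up to 2000 patients (section 6.2), 5 years each (section 6.4), annual drop-out d of 20% to 30% (section 10.1). Assumptions: a constant hazard, and every drop-out is a drug stop with the patient still observed to month 60.

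- Planned time: 2000 × 5 = 10,000 patient-years.
- Patients remaining at month 60: 2000 × (1 − d)^5 = 655 (d = 0.20) or 336 (d = 0.30).
- Hazard: λ = −ln(1 − d) = 0.223 or 0.357.
- Time on drug: 2000 × (1 − (1 − d)^5)/λ. For d = 0.20, 2000 × 0.67232/0.22314 = 6,026. For d = 0.30, 2000 × 0.83193/0.35667 = 4,665.
- Time off drug before month 60: 10,000 − 6,026 = 3,974 (40%), or 10,000 − 4,665 = 5,335 (53%).

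The post-dose tail is still covered by 7.4 and must come off. Its length is max(30 days, 5 × half-life). For an assumed half-life of 6 to 30 days it is 30 to 150 days. With w the tail in years and T = 5 − w, the remaining time is 2000 × (T − (1 − e^(−λT))/λ):

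| Tail | d = 0.20 | d = 0.30 |
|---|---|---|
| 30 days | 3,864 | 5,199 |
| 150 days | 3,435 | 4,662 |

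Under these assumptions, about 3,400 to 5,200 of the 10,000 planned patient-years lie inside section 9 but outside 7.4.

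**The case against.** The strongest reply is that the two windows govern partly different duties and can be read together. Section 7.4 concerns reporting to the sponsor, and section 9 concerns documentation. Section 8 has all case report form data forwarded to the sponsor and the biometrician, with adverse event forms checked for gaps and queried. Nothing in 7.4 cancels section 9. On that reading a late serious event still reaches the analysis. In 7.5, under a heading about serious events, severe looks like a slip of wording.

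Much of this stands. A reader might infer that late events, and serious events of low intensity, will be lost. The documents do not support that, because 7.5 requires notification of every serious event and section 9 requires its documentation to month 60. A reader might also infer that patients who stopped because of harm are followed least; sections 6.4 and 9 set 60 months regardless of stopping. Nor can 7.4 be said to close shortly after the last dose: without a half-life, only the 30-day minimum is certain.

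The 40% to 53% is not an estimate either. Section 10.1 uses the drop-out rate to argue that enough patients will have data at month 60, so its drop-outs are patients who no longer supply data. Time that nobody observes is covered by neither window in practice.

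The reply does not remove the inconsistency. The heading of 7.4 calls its window the collection period, so a site may reasonably take it as the limit for everything. Section 9 also describes the follow-up form as covering safety during therapy, which points the same way. The two meanings of the trigger in 7.5 remain whichever was intended.

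**Conclusion.** The protocol contradicts itself on when SAE collection ends, on the trigger for sending the form within 24 hours, and on what that form is for. These are inconsistencies in the current text, not matters left to the statistical analysis plan. The consequence that the text supports is late or inconsistent reporting between sites, and uneven ascertainment off drug in the long-term safety rates.

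The size cannot be derived, because the protocol does not separate drug stops from loss to follow-up. The bound of 40% to 53% of planned patient-years, or 34% to 52% after the tail, rests on all drop-outs being observed drug stops, a constant hazard, full enrolment and, for the tail, an assumed half-life. The true amount is smaller whenever some drop-outs are lost to follow-up. The point should be fixed, but the remaining duties in 7.5 and section 9 keep it from being critical.

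**What to change.** 1. Reconcile 7.4 with section 9 so that one SAE window applies to both reporting and documentation. It should state that patients who have stopped adalimumab but remain under observation are covered to month 60.
2. Define the end of that window for patients still on drug at month 60. Taking the later of month 60 and the post-dose period is not enough, because a patient who continues prescribed treatment would then have no fixed end.
3. In the last sentence of 7.5, replace severe with serious.
4. Describe the use of the ADR form in 7.5 in the same terms as section 9.

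The cost is protocol wording, a letter to sites and some additional SAE reports from patients who stopped. Late events that go unrecorded in the meantime may not be recoverable afterwards.

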7.5 Serious Adverse Event Reporting

In the event of a serious adverse event, whether related to Abbott product or comparator, (if applicable) or not, the physician will notify the Abbott contact person identified below within 24 hours of the physician becoming aware of the event.

Any adverse drug reaction that occurs is recorded by the treating physician using a separate "Adverse drug reaction report" form, labeled 'Bericht über unerwünschte Arzneimittelwirkungen'.

In case of a severe adverse event this form is sent by the treating physician within 24 hours to [name], Abbott GmbH & Co. KG, [name], [contact], [contact]).

7.6 Pregnancy Reporting

In the event of pregnancy, the physician will notify the Abbott contact person identified in Section 7.5 within 24 hours of the physician becoming aware of the pregnancy

8 Ethics and Quality

The German Drug Law defines an observational study as a data collection on routine use of medication, prescribed in the usual manner in accordance with the terms of the marketing authorization. In accordance to the code of contact of the German pharmaceutical industry the PMOS study protocol as well as the patients information and consent form will has been forwarded to the ethics committee of the German principal coordinating investigator [name]. [name]/Mainz for approval. The investigator will document the patients written consent and authorization to use and/or disclose personal and/or health data in the patients chart.

All patient data entered in the patient's case report form will be forwarded - without naming the patient - for evaluation to Abbott GmbH & Co KG and the biometrician online or in paper version. Each case report form bears a pre-printed patient identity number, which replaces the patient's initials. The date of birth will be replaced by the

patient's age at the start of the study. Accordingly, the patient's identity will not be disclosed to Abbott GmbH & Co. KG.

The data collection forms inclusive adverse event and serious adverse drugs reaction forms will be checked during data entry for missing or inconsistent data. These data will be completed through the use of data queries, if possible.

9 Case Report Forms

See also **6.5 Study conduct** for details

Data will be collected online or in paper version. The study comprises 4 different questionnaires to collect baseline data, data on therapeutic efficacy and safety during therapy with HUMIRA®, a final report on efficacy and safety and a patient questionnaire (German S-IBDQ).

Each study center receives either online permission to a database or binders with a set of sheets for data collection, depending on the technical equipment of the centre. The required data should be entered in to the data sheets using the physicians' documentation. Any observation of an adverse event in the time period up-to 60 months, beginning with the initiation of HUMIRA® therapy, must be documented on the "Adverse Event Form", labeled 'Bericht über unerwünschte Ereignisse' and checked for severity. If the event fulfills the serious criterion (Serious Adverse Event) the "Adverse drug reaction report" form, labeled 'Bericht über unerwünschte Arzneimittelwirkungen' must be completed in addition.

10 Data Analysis Plans

All statistical analysis procedures are described in detail in a statistical analysis plan. This plan will be established by the biometric before the database will be opened for the first interims analysis, and signed by the sponsor, the principle investigator and the biometric.

10.1 Sample size calculation

For this postmarketing observational study no sample size calculation was performed. The sample size of 2000 should lead to a sufficient number of patients with data at month 60 to perform adequate long-term safety and effectiveness analysis, assuming an annual drop-out rate of 20% to 30%.

10.2 Study population

The study population contains data of all documented patients. According to chapter 5 the objective of the study is the Adalimumab therapy in patients with Crohn's disease under routine conditions. Therefore a separate analysis for intention to treat population and per protocol population is not planned.

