with the terms of the marketing authorization. Data on the safety and efficacy of Adalimumab will be collected from initial dosing and up to 60 months of therapy.

Well-designed observational cohort studies including a very strict study protocol and monitoring, are indispensable to complement the knowledge gained from randomized controlled trials with important real-life data. The gain in experience was recently demonstrated in the German register RABBIT in rheumatoid arthritis patients. RABBITT provided information that the majority of patients with various comorbidities, concomitant medications, dosing schemes, and disease states, who would not fulfill the inclusion criteria of a major trial, benefit from biologic therapy (14).

5. Study Objective

The primary objective of the non-investigational study (PMOS) is to demonstrate long-term efficacy and safety of Adalimumab in patients with Crohn's disease under routine conditions and to evaluate the proportion of patients achieving remission and the time to remission induction.

Secondary objectives include: Improvement/resolution of signs and symptoms of the acute Crohn's disease (CDAI –100), rate of adverse events, and long-term improvement of patients QOL.

Further, the observation study protocol enables physicians to characterize patients that fulfill criteria for Adalimumab treatment thus ensuring the requirements of reimbursement.

6. Investigational Plan

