6.1 Selection of the Study Population

The study population will consist of patients with severe Crohn's disease.

Inclusion criteria: The inclusion criteria are as stated in the German Summary of Product Characteristics (SPC) 'Fachinformation' for $HUMIRA^{@}$

Exclusion criteria: The exclusion criteria are as stated in the German Summary of Product Characteristics (SPC) 'Fachinformation' for HUMIRA®

No additional inclusion and exclusion criteria are applicable since this project is non-interventional and Adalimumab will be used in a normal clinical setting according to the approved label.

Patients must provide the written informed consent to the investigator before entry into the PMOS.

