6.2 Number of Patients to be Enrolled

The PMOS will include up to 2000 patients with active moderate to severe Crohn's disease.

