6.5 Study Conduct

This postmarketing observational study will be conducted in a single-arm, multi-center format.

6

Observational studies are intended to gather findings in the use of marketable medicinal products. Their special feature is that they do not influence, as far as this is possible, the physician in charge of the treatment in his diagnosis or choice and implementation of therapy for the individual case.

Adalimumab must not be prescribed for the purpose of including a patient in this observational study. Physicians are encouraged to treat their patients as in routine clinical practice. The patient is only identified for the study after the decision on the therapy had been made.

Patients who have active severe Crohn's disease and start treatment with Adalimumab in normal clinical settings according to label are documented. Adalimumab will be administered by sc injection. The dose regimen is recommended following the approved label: Either an initial dose of 160 mg adalimumab sc at Week 0 followed by 80 mg adalimumab sc at Week 2, or an initial dose of 80 mg adalimumab sc at Week 0 followed by 40 mg adalimumab sc at Week 2. Starting at Week 4 all subjects will receive 40 mg every other week (eow) sc in an open-label fashion. The PMOS documentation starts with the first application of Adalimumab, and is repeated at month 3, 6, 9, 12, 18, 24, 30, 36, 42, 48, 54, and 60.

The follow-up observation period is planned for five years and is focused on maintenance of efficacy and safety information during normal clinical settings. The physicians will follow up the patient via regular office visits at intervals as determined by routine clinical practice or as recommended by national guidelines. It is expected that follow up visits will be performed every three months during the first year and every six months during the subsequent four years. Baseline and follow up visits will be reported on different forms. Failure to observe these usual practice intervals of patient visits will not constitute a breach or violation of the protocol.

The following data will be documented (if assessed in routine care):

Baseline Demographic Data (month 0)

Age

Gender

Height

Weight

Smoking behavior

Informed Consent

Informed consent signed by patient

Medical History

History of Crohn's disease

- Date of first diagnosis
- First manifestation of Crohn's disease

Local of luminal disease

Fistula

Stenoses

Extra-intestinal manifestation

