10.4 Biometric concept

The aims of the biometric concept for the statistical analysis include:

- Assessment of the safety of the Adalimumab therapy by evaluation and registration of side effects
- Assessment of the efficacy of the Adalimumab therapy by evaluating the proportion of patients achieving remission (remission as defined according to CDAI or HBI scores)
- Assessment of factors of influence to remission (logistic regression models), e.g. duration of therapy, concomitant medication in the medical history, extraintestinal manifestation, kind of Crohn's disease (fistula, stenoses)
- Assessment of the duration until remission
- Assessment of factors influencing time until remission (Cox regression models)
- Assessment of centre effects
- Subgroup analyses based on the results of the regressions analyses

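### Remission and CDAI −100 are not conditioned on activity at baseline, so any patients who start below the remission cut-off can raise the remission rate and lower the response rate

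*Protocol*

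**What the plan says.** **Entry.** Section 6.1 of the protocol takes eligibility from the product label and adds nothing: "No additional inclusion and exclusion criteria are applicable since this project is non-interventional". Activity is described in words. Section 6.2 says "The PMOS will include up to 2000 patients with active moderate to severe Crohn's disease", and section 6.5 says "Patients who have active severe Crohn's disease and start treatment with Adalimumab in normal clinical settings according to label are documented". Neither section, nor 6.1, requires a CDAI or HBI value.

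**Baseline score.** CDAI is on the baseline list in section 6.5, but under the condition "The following data will be documented (if assessed in routine care". HBI is not on that list.

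**Outcomes.** The primary objective (section 5) is partly to "evaluate the proportion of patients achieving remission and the time to remission induction". Section 10.4 repeats it: "Assessment of the efficacy of the Adalimumab therapy by evaluating the proportion of patients achieving remission", with remission scored by CDAI or HBI. It adds logistic models for remission and Cox models for time to remission, and names fistula, stenoses and extra-intestinal manifestations among the candidate factors. A CDAI fall of 100 points is a secondary objective.

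**Population.** Section 10.2 states: "The study population contains data of all documented patients". It rules out separate intention-to-treat and per-protocol analyses and names no other set.

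**The concern.** Achieving or inducing remission is a transition. A patient whose score is already below the cut-off at baseline cannot make it. If that patient stays in the denominator, a low score at a later visit counts as a success although nothing was induced. In the time-to-event analysis the patient was never at risk, yet contributes an event at the earliest time the visit schedule can record. For CDAI −100 the same patient has few points to lose and is close to a certain non-responder.

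The two efficacy measures would then move in opposite directions for a reason unrelated to the drug. The regressions in 10.4 are exposed as well. If patients treated mainly for a fistula, a stenosis or extra-intestinal disease tend to start with lower scores, those features could appear to predict remission only because of where the patients began. Section 10.4 then bases subgroup analyses on these models.

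**Working it through.** **Is the route in real?** The protocol has no score check at entry, and a clinical judgement of active disease does not guarantee a CDAI or HBI above a given value. Several entries in the protocol make low starting scores plausible:
- Fistula, stenoses and extra-intestinal manifestations are recorded at baseline (section 6.5), so patients whose main problem is not captured well by the score are expected.
- The baseline form asks for the former maintenance dose of patients with prior adalimumab, and asks for tuberculosis diagnostics only where therapy is recent (section 6.5). Both suggest that some patients are not new starters.
- Centres from a Phase IIIb Crohn's study are offered follow-up here (section 6.5.1).

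None of these gives a number of patients.

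**Plan's own figure.** The protocol states no remission rate, response rate, remission cut-off or share in remission at baseline, so there is nothing to reproduce. All four rates below are assumptions.

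**Inputs.** p = share below the cut-off at baseline; m = share of those below it at the visit; r = remission rate in patients active at baseline; q = CDAI −100 response in patients active at baseline. Response in the already-low group is set to zero.

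**Formulas.**
- Reported remission = p·m + (1 − p)·r, so the bias is p(m − r). It is upward whenever m exceeds r.
- Reported CDAI −100 = (1 − p)·q, so the bias is −p·q.

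**Results with r = 40%, q = 50%.**

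| p | Remission, m = 70% | Remission, m = 100% | CDAI −100 |
|---|---|---|---|
| 0% | 40% | 40% | 50% |
| 5% | 41.5% | 43% | 47.5% |
| 10% | 43% | 46% | 45% |
| 20% | 46% | 52% | 40% |
| 30% | 49% | 58% | 35% |

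For p = 10% and other values of r, the rise is 0.10 × (m − r). At m = 100% this is 7, 6 or 5 points for r = 30%, 40% or 50%; at m = 70% it is 4, 3 or 2 points. The fall in CDAI −100 is 0.10 × q, which is 4 to 6 points for q = 40% to 60%.

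**Why response is set near zero.** Assume a cut-off of CDAI 150, which is not in the protocol. A patient starting at 149 must reach 49 or less, one at 120 must reach 20 or less, and one at 100 must reach 0. From 80 the target is −20.

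**Effect on a regression factor.** Suppose r = 40% with and without fistula, so that there is no true difference, but p is 30% with fistula and 5% without. With m = 100%, reported remission is 58% against 43%, an odds ratio of (0.58/0.42)/(0.43/0.57) = 1.83. With m = 70% it is 49% against 41.5%, an odds ratio of (0.49/0.51)/(0.415/0.585) = 1.35. Both come from the baseline mix alone.

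**After the fix.** Restricting the set to patients above the cut-off at baseline sets p to zero, and the estimates return to r and q among patients with a recorded baseline score.

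**The case against.** The best defence has four parts.

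1. *Section 10.2 does not place every patient in every denominator.* This is right. A reader might infer that the protocol expressly fixes one risk set for all outcomes, but it only names the population and rules out an intention-to-treat and per-protocol split. The words for achieving and inducing remission even suggest a change from active disease. What stands against this is that no condition on baseline status appears in sections 5, 10.2 or 10.4, and the only population offered is everyone.

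2. *The statistical analysis plan will settle it.* It may, and denominators often belong there. But section 10.3 expressly defers minimum documentation to that plan, whereas 10.2 states the population and defers nothing. A restriction found only there would narrow what the protocol says.

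3. *The protocol requires active disease.* It does, in sections 6.2 and 6.5, and the label is described in the rationale as covering severe active disease. This limits the problem and may make p small. It does not remove it, because no score backs the words.

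4. *A restricted set has its own selection.* This also stands. Baseline CDAI may be missing and HBI is not on the baseline list, so an unknown number of patients could drop out of the analysis.

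The study has a single arm, so no between-arm comparison is biased. The absolute remission proportion is itself the result, however, and its denominator matters for that reason.

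**Conclusion.** The point holds as a gap in how the efficacy population is fixed. All documented patients is the only stated population, no baseline condition is attached to remission, time to remission or CDAI −100, and no score is required at entry. The direction follows from the formulas: remission up when m exceeds r, CDAI −100 down, time to remission shorter. The size does not follow from the documents, because p, m, r, q and the cut-off are all assumed.

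Two stronger readings are not supported. One is that the study's remission figure will be inflated by a definite amount; the share of affected patients is unknown, and the requirement of active disease may keep it low. The other is that such patients are in remission by definition at the first follow-up visit. That is so only if the baseline score itself is counted or the score stays low, which is why m is allowed to be below 100%. The issue merits an amendment but does not invalidate the design.

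**What to change.** Amend section 10.2 as follows:
- Keep all documented patients for safety and for description.
- Make the analysis set for remission, time to remission, their regressions and CDAI −100 the patients with a recorded baseline score above the remission cut-off, on the same scale as is used at follow-up. CDAI −100 needs a baseline CDAI.
- Report patients below the cut-off at baseline separately, as remission maintained or lost.
- Give the number of patients without a usable baseline score, and show the all-patient result as a sensitivity analysis.

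The baseline CDAI is already on the form. Patients scored only by HBI at follow-up need a baseline HBI, which the section 6.5 list does not contain; without one they fall into the counted group.

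The cost is a smaller denominator, possible selection through missing baseline scores, and a probably less favourable remission figure. The sensitivity analysis makes the first two visible. Eligibility, treatment and the non-interventional design do not change.
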